4.5. Multiple Comparisons

Each group of endpoints for this study contains three hypothesis tests based on the study treatment: i) AD109 vs placebo, ii) AD109 vs R-oxybutynin, iii) AD109 vs atomoxetine. The type I error will be controlled by a fixed sequence procedure in which the hypothesis tests are conducted in the following order: i) AD109 vs placebo, ii) AD109 vs R-oxybutynin, iii) AD109 vs atomoxetine. Primary and secondary endpoints will be tested sequentially in the order they appear in Section 2.2.1 and Section 2.2.2. All hypothesis tests will test that the two-sided p-value is less than 0.05. All hypothesis tests for secondary endpoints will also be reported using the nominal 0.05 two-sided alpha level.

4.6. Data Derivations and Transformations

Study Day will be calculated as:

- Date of assessment – date of randomization + 1 for assessments done on or after date of randomization
- Date of assessment – date of randomization for assessments done before date of randomization

For each efficacy and safety endpoint, the baseline value will be calculated as the last non-missing value prior to randomization (except where unscheduled assessments are performed the baseline value should be the value recorded at Screening). Where applicable, change from baseline values will be calculated as:

$$\text{Change from Baseline} = \text{assessment value} - \text{baseline value},$$

while the percent change from baseline values will be calculated as:

$$\text{percent change from baseline} = \frac{\text{change from baseline}}{\text{baseline value}} \times 100\%.$$

For the endpoints that look for the proportion of participants with $\geq 50\%$ reduction, participants will be assigned a visit level indicator:

$$\text{Indicator of } \geq 50\% \text{ reduction} = \begin{cases} 1 & \text{if percent change from baseline } \leq -50\% \\ 0 & \text{otherwise} \end{cases}$$

4.7. Repeated Measure Modeling for Select Endpoints

In Section 6, modeling will be used for comparisons between study treatments with respect to given endpoints using the PROC GLIMMIX procedure in SAS. The model will include study treatment and visit as fixed effects. Within participant variability (nested within treatment

sequence) will be modeled using an unstructured (e.g., TYPE = UN, CHOL) covariance pattern. The unstructured covariance parametrized through its Cholesky root is to be used for logistic regression models and models in which convergence fails for the completely unstructured covariance. Point estimates (e.g., mean, difference of means) and inferential statistics (e.g., confidence interval, p-values) will be provided using least square (LS) methods. Unless otherwise stated, the link will be identity and the distribution gaussian.

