4.1. Data Quality Assurance

Once all the source verification is complete, all queries are resolved, and the database has been

updated appropriately, the database will be locked and made available to CTI Biostatistics for final analysis.

Data may be made available to CTI Biostatistics for programming purposes prior to database lock at a time when source verification and query resolution is ongoing.

All SAS programs used to create analysis data sets, tables, and listings will be independently programmed by two individuals. The independent SAS outputs produced will be compared, and the SAS programs will be updated until the outputs match.

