6.1. Primary and Secondary Efficacy Analysis of HB(4%)

Comparisons will be performed as described in Section 4.5. A repeated measures model (see Section 4.7) will be used to model change in $\log_{10}(\text{HB}[4\%] + 1)$ from baseline. Model based LS mean estimates will be provided for the following:

- mean change from baseline by study treatment (AD109, placebo, R-oxybutynin, and atomoxetine),
- difference in mean change between AD109 and the other three treatments (placebo, R-oxybutynin, and atomoxetine) with 95% confidence interval and respective p-values (for the null hypothesis).

If the model shows there is a visit (i.e., period) effect, then ad hoc analyses will be performed. A sensitivity analysis will be performed using the PP Set on the primary efficacy endpoint using the same methods described above and using HB(4%) with identity transform (i.e., without transform) on the mITT set.

Descriptive statistics for the reported $\log_{10}(\text{HB}[4\%] + 1)$ value and change from baseline in

$\log_{10}(\text{HB}[4\%] + 1)$ will be presented by study treatment. By taking the inverse transformations of the respective means, the geometric mean of $\text{HB}(4\%) + 1$ and the ratio of the geometric mean to baseline will be reported.

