6.2. Additional Secondary Efficacy Analysis

6.2.1. AHI(4%)

Multiple comparisons will be performed as described in Section 4.5. A repeated measures model will be used to model change in AHI(4%) from baseline. Model based LS mean estimates will be provided for the following:

- mean change by study treatment (AD109, placebo, R-oxybutynin, and atomoxetine),
- difference in mean change between AD109 and the other three treatments (placebo, R-oxybutynin, and atomoxetine) with 95% confidence interval and respective p-values (for the null hypothesis).

Descriptive statistics for the reported AHI(4%) value and change from baseline in AHI(4%) will be presented by study treatment.

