7.4. DSST

A repeated measures model (see Section 4.7) will be used to model the natural log of total number of the correct symbol assignments¹ (log (total completed - total incorrect)) from the DSST.

Exponentiation of the model-based LS mean estimates of log values will be used to provide the following:

- Geometric mean of DSST by study treatment (AD109, placebo, R-oxybutynin, and atomoxetine), and
- Ratio of (geometric) mean of DSST between AD109 and the other three treatments (placebo, R-oxybutynin, and atomoxetine) with the 95% confidence intervals.

Descriptive statistics of DSST and a by-participant listing (with both raw values and natural log of total complete) will also be provided.

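### SAP 4.7 sets no small-sample standard-error or degrees-of-freedom method for its unstructured covariance and does not name the matrix index; read by visit and uncorrected, the 5% tests run at about 6-8%

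*SAP*

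**What the plan says.** SAP 4.7 is the whole specification of the repeated-measures model. It names PROC GLIMMIX and states: "The model will include study treatment and visit as fixed effects". The covariance sentence begins "Within participant variability (nested within treatment" and ends "sequence) will be modeled using an unstructured (e.g., TYPE = UN, CHOL) covariance pattern". Estimates, intervals and p-values are to come from least-squares means. The section names no effect that indexes the matrix, no degrees-of-freedom method and no standard-error correction. SAP 4.5, 6.1, 6.2 and 7.4 and Protocol section 8 do not supply them either.

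The model is used widely:
- SAP 6.1 uses it for HB(4%), on the log scale.
- SAP 6.2.1 says "A repeated measures model will be used to model change in AHI(4%) from baseline", and 6.2.2 and 6.2.3 do the same for ODI(4%) and time with SaO2 below 90%.
- SAP 7.4 says "A repeated measures model (see Section 4.7) will be used to model the natural log of total number" of correct DSST symbols.

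The testing rule in SAP 4.5 is a fixed sequence starting with AD109 vs placebo, and "All hypothesis tests will test that the two-sided p-value is less than 0.05".

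**The concern.** In a crossover with 24 sequences (SAP 3.2.1), a matrix indexed by visit and one indexed by treatment are different models. If it is indexed by visit, the estimated covariance determines how each participant's visits are weighted in the treatment contrast. The ordinary model-based standard error treats those weights as known, which makes it too small in a sample of this size. If it is indexed by treatment, this barely happens.

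SAP 4.5 depends on each test holding 0.05, and AD109 vs placebo on HB(4%) opens the sequence. The two component contrasts that follow carry the combination-drug claim.

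No planned check would expose the problem. The per-protocol check reuses the model ("A sensitivity analysis will be performed using the PP Set on the primary efficacy endpoint using the same methods described above"), and the untransformed HB analysis names no other model. Under the double-programming rule, "the SAS programs will be updated until the outputs match". That makes two programmers agree on a coding but does not fix it in advance. SAP section 4 requires departures from the SAP to be reported, but choosing an option the SAP never named is not a departure.

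**Working it through.** **The plan's own figure.** Inputs from Protocol 8.1 and SAP 9: difference 3.7, SD 9, two-sided 0.05, 80% power, discontinuation below 20%. The paired formula gives n = (9 × (1.960 + 0.842) / 3.7)² = 46.4 completers, and 46.4 / 0.8 = 58. Power is 79.6% at 46 completers. So 58 reproduces, and 46 is the completer count at the dropout limit. This takes 9 as the SD of the paired difference, although the documents call it the within-subject SD. That is a separate matter.

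**Simulation under the null.** Normal data, balanced draws from the 24 sequences, treatment and visit effects, REML, correlation 0.5, equal SDs. There were 20,000 trials per cell, with Monte Carlo error about 0.15-0.19 points. The settings were 46 complete, 58 complete, and 58 with 20% dropout equally likely after visit 1, 2 or 3. The documents give no covariance and no dropout timing, so both are assumptions. Ranges cover the three AD109 contrasts and the three settings. The uncorrected rows also cover three df choices: participants minus 1, residual, and participants minus 24 sequences.

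| Index | SE and df method | Rejection rate at nominal 5% |
|---|---|---|
| Visit | uncorrected | 6.3-8.0% |
| Visit | Satterthwaite df only | 7.0-7.9% |
| Visit | Kenward-Roger | 5.1-5.5% |
| Treatment | uncorrected | 4.4-5.6% |
| Treatment | Kenward-Roger | 4.8-5.2% |

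**Cross-check by hand.** Indexed by visit, the mean model SE divided by the empirical SD of the estimate was 0.896-0.926, which is about 7-10% too small. With 148 df the critical value is 1.976, and the effective cut-off is 1.976 × 0.896 = 1.77 to 1.976 × 0.926 = 1.83. The two-sided t tail areas are 7.9% and 6.9%, which match the Satterthwaite row. A better df alone does not help because the error lies in the SE.

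**Other covariances.** A second, separately programmed simulation used 2,000-3,000 trials per setting. It covered compound symmetry with correlation 0.3, 0.6 and 0.85, first-order autoregressive correlation 0.7 over visits, and SD rising over visits. Averaged over the three contrasts:
- by visit, uncorrected: 5.9-8.1%
- by visit, Kenward-Roger: 5.0-5.8%
- by treatment, uncorrected: 4.4-6.2%
- by treatment, Kenward-Roger: 4.6-5.5%

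**If SDs differ by treatment** (assumed ratios; Kenward-Roger throughout; 58 with 20% dropout; 10,000 trials, Monte Carlo error about 0.2-0.3 points):

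| AD109 SD relative to the others | By visit | By treatment |
|---|---|---|
| 1.5× | 8.1-8.2% | 5.2-5.3% |
| 1.25× | 6.7-7.0% | 4.9-5.1% |
| 0.8× | 4.2-4.4% | 4.7-5.1% |
| 0.67× | 3.7-4.0% | 4.9-5.1% |

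With assumed SDs of 0.7, 0.8, 1.2 and 1.2 for AD109, atomoxetine, R-oxybutynin and placebo, by visit with Kenward-Roger gave about 1% for AD109 vs atomoxetine and 5.4-6.4% for the other two contrasts. The level can therefore err in either direction.

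**If variance or correlation changes over visits** (also assumed), treatment indexing keeps its level but can lose precision. The empirical SD of the contrast was larger than with visit indexing by:
- 12% under autoregressive correlation 0.7
- 5% with first-visit SD 1.5×
- 7% with SD rising from 1 to 1.8

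From 80% power, Φ(2.80 / 1.12 − 1.96) = 71%, a loss of about 9 points. The other two cases lose about 4 and 6. Under compound symmetry, treatment indexing was about 4% more precise.

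**The case against.** The strongest reply is that the SAP never says it will use uncorrected standard errors by visit. An experienced programmer could add Kenward-Roger or index by treatment, and either would bring the equal-SD rate close to 5%. Even the worst reading adds only about 1.3-3.0 points. This stands as a limit on the claim, but it does not supply the missing specification. Visit is the likelier index, because the section is titled as repeated-measures modelling and SAP 6.1 equates visit with period. A plan followed on that reading without a correction would exceed its level.

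Four stronger readings are tempting, and the documents do not support them.
- A reader might infer that the trial's type I error is 6-8%. The SAP fixes no such rate.
- A reader might rank the index as the main omission. That follows only from assumed SD ratios between treatments. With equal SDs, Kenward-Roger alone repairs visit indexing.
- A reader might take the 4-6% for treatment indexing as certain to hold, or take treatment indexing as plainly better. Uncorrected, it varied with the df choice, and its precision cost against visit indexing can be material.
- The nesting phrase might suggest a participant random intercept. A single intercept has one variance, so an unstructured or Cholesky form would say nothing about it. That reading is strained.

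**Conclusion.** The omission is real and worth closing as a cheap improvement. On the more natural reading (indexed by visit, uncorrected model-based SE), the nominal 5% tests run at about 6-8% because the SE is about 7-10% too small. Indexed by treatment, they run at about 4-6%. Both figures assume normal data and SDs that do not differ by treatment. The correlation and dropout patterns are also assumed, because the documents give none. The 6-8% belongs to one reading that the SAP leaves open. Nothing is claimed about the logistic models of SAP 6.2.4, which were not simulated.

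**What to change.** In SAP 4.7:

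1. Pre-specify Kenward-Roger standard errors and degrees of freedom (DDFM=KR) for all Gaussian models. Satterthwaite df alone is not enough if the matrix is indexed by visit.
2. State which effect indexes the unstructured matrix. This is the sponsor's choice and a trade-off. Treatment indexing protects the level if SDs differ by treatment. Visit indexing can be more precise if variance or correlation changes over visits.

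The cost is two sentences and one SAS option. If indexed by visit, intervals become about 4.5-10% wider than the uncorrected ones, depending on the df replaced, which is close to their correct width. If indexed by treatment, they widen by at most about 2.4%. No change to design, data or conduct is needed.

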5. STUDY PARTICIPANTS

5.1. Disposition of Participants

A table of frequency counts and percentages of all participants who are enrolled, randomized, and included in each analysis set will be provided. Participant disposition including study completion status and reasons for early termination will be tabulated overall. A by-participant listing will be provided.

5.2. Protocol Deviations

Two separate by-participant listings for major and minor protocol deviations will be provided.

5.3. Demographic

Descriptive statistics will be used to summarize the demographic characteristics (age, gender, race, ethnicity, height, weight, and BMI) overall using the Safety Set. A by-participant listing will also be provided.

5.4. Baseline Characteristics

The results of the following assessments completed during the baseline PSG (PSG-0) will be summarized overall using the Safety Set:

- AHI(4%)
- ODI(4%)
- HB(4%)
- Total time with $\text{SaO}_2 < 90\%$
- Snoring index
- Arousal indices (respiratory and spontaneous)
- Fraction of hypopneas
- WASO
- Sleep stage (N1, N2, N3, R) separately in minutes and percent of total sleep time
- Sleep efficiency
- Number of awakenings
- Sleep onset latency

- Heart rate
- Total sleep time
- Systolic blood pressure
- Diastolic blood pressure

Additionally, the Epworth sleepiness scale total score will be summarized.

A by-participant listing will also be provided for Epworth sleepiness scale. The baseline PSG parameters and vital signs will be included in their respective general listings.

5.5. Medical History

All medical conditions and surgical procedures will be coded using the Medical Dictionary for Regulatory Activities (MedDRA) version 23.0. The number and percent of participants with each medical condition and surgical procedure will be presented by MedDRA system organ class (SOC), preferred term (PT) overall for the Safety Set. Each participant will be counted only once per SOC and PT. A by-participant listing will also be provided.

5.6. Prior and Concomitant Medications

Prior and concomitant medications will be coded using the September 2020 B3 Global World Health Organization (WHO) Drug Dictionary version. The number and percent of participants using each medication will be tabulated by Anatomical Therapeutic Chemical (ATC) level 3 and preferred name overall. Each prior or concomitant medication reported more than one time will only be counted once per participant for each ATC level and preferred name. A by-participant listing will also be provided.

6. EFFICACY ANALYSIS

The mITT Set will be used for all efficacy analyses.

6.1. Primary and Secondary Efficacy Analysis of HB(4%)

Comparisons will be performed as described in Section 4.5. A repeated measures model (see Section 4.7) will be used to model change in $\log_{10}(\text{HB}[4\%] + 1)$ from baseline. Model based LS mean estimates will be provided for the following:

- mean change from baseline by study treatment (AD109, placebo, R-oxybutynin, and atomoxetine),
- difference in mean change between AD109 and the other three treatments (placebo, R-oxybutynin, and atomoxetine) with 95% confidence interval and respective p-values (for the null hypothesis).

If the model shows there is a visit (i.e., period) effect, then ad hoc analyses will be performed. A sensitivity analysis will be performed using the PP Set on the primary efficacy endpoint using the same methods described above and using HB(4%) with identity transform (i.e., without transform) on the mITT set.

Descriptive statistics for the reported $\log_{10}(\text{HB}[4\%] + 1)$ value and change from baseline in

$\log_{10}(\text{HB}[4\%] + 1)$ will be presented by study treatment. By taking the inverse transformations of the respective means, the geometric mean of $\text{HB}(4\%) + 1$ and the ratio of the geometric mean to baseline will be reported.

6.2. Additional Secondary Efficacy Analysis

6.2.1. AHI(4%)

Multiple comparisons will be performed as described in Section 4.5. A repeated measures model will be used to model change in AHI(4%) from baseline. Model based LS mean estimates will be provided for the following:

- mean change by study treatment (AD109, placebo, R-oxybutynin, and atomoxetine),
- difference in mean change between AD109 and the other three treatments (placebo, R-oxybutynin, and atomoxetine) with 95% confidence interval and respective p-values (for the null hypothesis).

Descriptive statistics for the reported AHI(4%) value and change from baseline in AHI(4%) will be presented by study treatment.

6.2.2. ODI(4%)

Multiple comparisons will be performed as described in Section 4.5. A repeated measures model will be used to model change in ODI(4%) from baseline. Model based LS mean estimates will be provided for the following:

- mean change by study treatment (AD109, placebo, R-oxybutynin, and atomoxetine),
- difference in mean change between AD109 and the other three treatments (placebo, R-oxybutynin, and atomoxetine) with 95% confidence interval and respective p-values (for the null hypothesis).

Descriptive statistics for the reported ODI(4%) value and change from baseline in ODI(4%) will be presented by study treatment.

6.2.3. Total time with $\text{SaO}_2 < 90\%$

Multiple comparisons will be performed as described in Section 4.5. A repeated measures model will be used to model change in total time with $\text{SaO}_2 < 90\%$ from baseline. Model based LS mean estimates will be provided for the following:

- mean change by study treatment (AD109, placebo, R-oxybutynin, and atomoxetine),
- difference in mean change between AD109 and the other three treatments (placebo, R-oxybutynin, and atomoxetine) with 95% confidence interval and respective p-values (for the null hypothesis).

Descriptive statistics for the reported total time with $\text{SaO}_2 < 90\%$ value and change from baseline in total time with $\text{SaO}_2 < 90\%$ will be presented by study treatment.

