## 7.1.1 Polysomnography

- Methods: Standard overnight PSG recording and data interpretation will be performed in accordance with the American Academy of Sleep Medicine (AASM) scoring manual.
   Participants will be instrumented with standard PSG electrodes. Time of lights out will be established according to the participants' habitual schedule and kept constant across the PSG study nights. The participants will be given 8 hours of time-in bed.
- Scoring: All PSG studies (including screening PSG) will be scored by centralized PSG technologists, blinded to treatment assignment. Scoring will be conducted according to the American Academy of Sleep Medicine manual scoring criteria.

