2.2.3. Exploratory Endpoints

The exploratory efficacy endpoints are as follows:

- PSG sleep and arousal parameters
 - Sleep stages distribution and percentage of time in the various sleep stages
 - Sleep Efficiency (SE)
 - Wake After Sleep Onset (WASO)
 - Number of Awakenings (NAW)
 - Sleep Onset Latency (SOL)
 - Percentage of total sleep time (TST) spent in sleep stage N1 (Stage N1%)
 - Percentage of TST spent in sleep stage N2 (Stage N2%)
 - Percentage of TST spent in sleep stage N3 (Stage N3%)
 - Percentage of TST spent in sleep stage R (Stage R%)
 - Snoring index
 - Arousal indices (respiratory and spontaneous)
 - Fraction of hypopneas

- Alternate measures of AHI, ODI and HB
 - AHI(4%) in non-rapid eye movement (NREM) sleep
 - AHI(4%) in rapid eye movement (REM) sleep
 - AHI(4%) adjusted for position
 - AHI(3% or arousal)
 - HB(3% or arousal)
 - HB(Total)
 - ODI(3%)
- Subgroup analyses of efficacy endpoints in participants meeting “moderate collapsibility” criteria (AHI[4%] 10 to <20, or AHI[4%] ≥20 if any one of the following are met: F_{hypopnea} of >90% OR mean oxygen desaturation of obstructive events of ≤4% OR F_{hypopnea} of 50 to 90% and mean oxygen desaturation of 4 to 8%) at baseline (PSG-0).

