4.4.1. PSG Parameters

The criteria for use of PSG data will be as follows:

- When TST is < 120 minutes, only TST, time in bed, Stage N1%, Stage N2%, Stage N3%, and Stage R% will be reported. All other PSG indices will be excluded.

- Any AHI and HB parameters during REM will be reported only when the time spent in REM is > 5 minutes.
- Any AHI and ODI parameters in supine position will be reported only when the time spent supine is > 5 minutes.

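### Does testing total time with SaO2 below 90%, with no stated unit, counting window or percent-of-sleep analysis, call for a change to the SAP?

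*SAP*

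**What the plan says.** SAP 6.2.3 states: "A repeated measures model will be used to model change in total time with" SaO2 below 90%, with least-squares mean changes, differences from the three comparators, 95% confidence intervals and p-values. On the model, SAP 4.7 says "The model will include study treatment and visit as fixed effects". On testing, SAP 4.5 says "Primary and secondary endpoints will be tested sequentially in the order they appear in Section 2.2.1 and Section 2.2.2".

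The endpoint is also named in Protocol 3 and in SAP 2.1.2, 2.2.2, 2.2.4, 5.4 and 7.5. None of these gives a unit or says whether wake time counts, and the derivations in SAP 4.6 do not mention it.

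Three provisions bear on exposure time and scoring:
- Protocol 7.1.1: "The participants will be given 8 hours of time-in bed". The same section holds lights-out time constant across a participant's PSG nights.
- SAP 4.4.1: "When TST is < 120 minutes, only TST, time in bed, Stage N1%, Stage N2%, Stage N3%, and Stage R% will be reported".
- Protocol 7.1.1: "All PSG studies (including screening PSG) will be scored by centralized PSG technologists, blinded to treatment assignment".

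For sleep architecture the SAP does use sleep time as a denominator. The baseline table has "Sleep stage (N1, N2, N3, R) separately in minutes and percent of total sleep time", and each stage is an exploratory endpoint as a share of TST (SAP 2.2.3).

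**The concern.** This is the only continuous tested efficacy endpoint expressed as an absolute duration. HB is in %min/h, and AHI and ODI are indices. Eight hours in bed fixes the opportunity to sleep, not sleep itself, and the model has no term for sleep time. If one treatment shortens sleep, minutes below 90% can fall with no better oxygenation. The two scales can even point in opposite directions: 40 of 400 minutes is 10.0% and 36 of 340 minutes is 10.6%, so the second night is 4 minutes better but worse as a share of sleep.

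The undefined window adds to this, since two analysts could in principle count different things. What would be at stake is the reading of one secondary endpoint and its nominal p-values. Because that endpoint is in the fixed sequence, so is access to the responder endpoints listed after it.

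**Working it through.** The plan gives no mean, SD or power for this endpoint, and its sample-size statement concerns HB only. There is no planned figure to reproduce, so every sleep and desaturation input below is an assumption.

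**Place in the sequence (SAP 2.2.1, 2.2.2, 4.5).** HB 1 + 2, AHI 3, ODI 3: 1 + 2 + 3 + 3 = 9 tests come first. Time below 90% supplies tests 10 to 12. Three responder endpoints against three comparators follow (3 × 3 = 9, tests 13 to 21).

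**Range of sleep admitted.** Upper limit 8 × 60 = 480 minutes; lower limit 120 minutes from SAP 4.4.1. With 10% of sleep below 90%, that is 12 to 48 minutes (6 to 24 at 5%, 24 to 96 at 20%). These are limits over all possible nights. The crossover contrast depends on differences between treatments within a participant, which will be far narrower. Protocol 5.2 also excludes clinically significant insomnia, typical sleep under 5 hours and night or shift work.

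**Sleep loss with no drug effect, counted over sleep.** Let L be the fraction of sleep lost and k the desaturation rate in the lost sleep relative to the night's average. Ratio in minutes = 1 − kL. Ratio in percent of TST = (1 − kL)/(1 − L).

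| L | k | Minutes | Percent of TST |
|---|---|---|---|
| 0.10 | 0.5 | −5% | 0.95/0.90: +5.6% |
| 0.10 | 1 | −10% | 0% |
| 0.10 | 1.5 | −15% | 0.85/0.90: −5.6% |
| 0.15 | 0.5 | −7.5% | 0.925/0.85: +8.8% |
| 0.15 | 1 | −15% | 0% |
| 0.15 | 1.5 | −22.5% | 0.775/0.85: −8.8% |

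The two scales are equally far from no change when (1 − k)/(1 − L) = k, so k = 1/(2 − L): 0.53 for L = 0.10 and 0.54 for L = 0.15. Below that, minutes are closer to the truth; above it, the percentage is.

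**With a true 20% reduction and L = 0.15**, multiply by 0.8. Minutes show reductions of 26% (k = 0.5) to 38% (k = 1.5). Percent of TST shows 13% to 27%. Neither scale recovers 20% unless accrual is even, and then only the percentage does.

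**Does the window matter?** Let wake time accrue minutes below 90% at w times the sleep rate. With 10% of sleep below 90%, minutes over the time in bed = 0.10 × [TST + w(480 − TST)]. For TST falling from 400 to 340:
- w = 0: 40 to 34 (−15%), the same as counting sleep only.
- w = 0.5: 44 to 41 (−6.8%).
- w = 1: 48 to 48 (no change).

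So the choice of window changes the result only if wake contributes, and then the wider window depends less on sleep time. The table above is the least favourable case for the planned endpoint in this respect.

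**Unit.** Minutes versus hours divides estimates and standard errors by the same constant, so p-values are identical.

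**What the planned outputs show.** SAP 7.5 summarises TST and time below 90% by treatment in the same section and lists PSG values by participant. SAP 6.3 gives change in sleep efficiency, wake after sleep onset and sleep onset latency by treatment with 95% intervals. A sleep difference would be visible to anyone reading the result.

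**The case for a change.** The best case for a change is that the remedy costs little and the gap is real. One sentence would fix unit and window in both the efficacy and safety tables, and one derived variable would give the AD109 contrast per unit of sleep, which no planned output does. HB, AHI and ODI measure other quantities. The sponsor itself monitors sleep time by PSG and notes possible somnolence with both drugs (Protocol 7.2). Double programming (SAP 4.1) makes two programmers agree but does not prespecify the choice. The consequence also runs past tests 10 to 12, because failing there closes the sequence to the responder endpoints.

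What stands: the definition is not written down, the gating of the responder endpoints is correct, and descriptive TST does not apportion a difference in minutes.

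What does not stand is the step to a necessary change. Central scoring gives baseline and treatment nights a common source, and nothing suggests that the window would be chosen by treatment. A difference caused only by shorter sleep, with HB, AHI and ODI unchanged, would ordinarily stop the sequence before test 10. The percentage would carry no alpha, so it could not alter any test or reopen the sequence. Nor would it cleanly isolate oxygenation, because TST is itself measured after dosing. The sleep-stage precedent concerns sleep architecture, not oximetry.

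**Conclusion.** No change is called for. The missing unit has no inferential effect. The missing window is a scoring detail that central reading can be expected to settle alike for all nights, and it matters only if wake time contributes minutes below 90%. Absolute time is a legitimate estimand: it measures total hypoxaemic exposure over the night, as the protocol's endpoint list has it. A percent-of-TST display would be a reasonable optional extra. Its absence makes nothing in the planned analysis wrong.

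An assumed 10% to 15% sleep loss, with the lost sleep desaturating at 0.5 to 1.5 times the average rate and no drug effect, would move minutes by −5% to −22.5% and the percentage by up to about 9% either way. The documents state no sleep effect of any treatment, so neither size nor direction can be fixed. The primary HB analysis, the sample of 58 and tests 1 to 9 are untouched. Tests 10 to 12 and the responder tests behind them keep their error control under the plan as written. The conclusion assumes that one scoring definition is used for baseline and all four treatment nights, as central blinded scoring implies.
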